An innovative high strength, lithium disilicate ceramic material is reported to offer a more efficient fabrication process resulting in a similar esthetic and high strength crown. Lithium Disilicate Quartz (Ivoclar Vivadent) is a glass ceramic with crystalline phases of lithium disilicate and quartz.

Current glass ceramic materials have a recommended minimum thickness to maintain the maximum strength potential of the material. An occlusal thickness of 1.5 mm is generally recommended. This can be a challenge to achieve in the posterior of the mouth with teeth with limited clinical crown height. In addition, the glass ceramic material should be adhesively bonded to ensure maximum strength of the restoration. Lithium Disilicate Quartz offers an alternative high strength ceramic that may allow a more conservative occlusal reduction resulting in a crown thickness of 1.2 mm, equitable to the recommendation for full contour zirconia crowns. The material may also be sufficiently strong to allow for conventional cementation in addition to adhesive bonding.

Current high strength materials have not been embraced for partial coverage restorations due to the lengthy post-milling firing process. Lithium Disilicate Quartz may also offer a more clinical efficient process to fabricate partial coverage restorations since it does not require post-milling crystallization.

It is the intent of this investigation to evaluate the clinical application and performance of the new high strength, lithium disilicate quartz material for CAD/CAM-generated chair-side crown applications.

5 Summary of Objectives and Design

This investigation will be a randomized, prospective, longitudinal clinical trial to study the clinical performance of a new monolithic, high strength precrystallized lithium disilicate material for chairside CAD/CAM crowns. The restorations will be evaluated for a period of five years.

6 Specific Aims

The specific aims of this project are:

1. Evaluate the short-term post-operative sensitivity associated with cementation techniques using a self-adhesive, self-curing resin cement and a total etch/universal bonding agent with a dual-cured resin cement.
2. Evaluate the resistance to material chipping and fracture of reduced thickness high strength precrystallized lithium disilicate CAD/CAM crowns.

3. Evaluate the longitudinal clinical performance of precrystallized lithium disilicate crowns over five years of clinical service. The crowns will be evaluated with modified FDI criteria for maintaining their esthetic, functional and biological properties.

7 Research Plan: Methods and Materials

7.1 Subjects

The patient population will be selected from current patients under clinical treatment at the University of Michigan Dental Clinics. Patients will be at least 18 years of age, of either gender, and of any ethnic background. Each patient should have at least one carious lesion or defective restoration to be restored on a maxillary or mandibular premolar or molar tooth. Each lesion or defective restoration should exhibit sufficient size or loss of tooth structure requiring a full crown restoration. The tooth should have at least one opposing tooth in occlusion and one adjacent tooth with an intact proximal contact. All teeth will test vital and be asymptomatic at the beginning of treatment. No more than two restorations will be placed per patient. If a patient presents with more than two acceptable teeth for the study, molar teeth will be included prior to premolar teeth. Exclusion criteria will include:

- Devital or sensitive teeth
- Teeth with prior endodontic treatment of any kind
- Teeth with a history of direct or indirect pulp capping procedures
- Patients with significant untreated dental disease to include periodontitis and/or rampant caries
- Women who self-report that they are possibly pregnant, pregnant, or lactating, as elective dental treatment is not indicated at these times
- Patients with a self-reported past history of allergies to the materials to be used in the study including composite resin cements or ceramic restorative materials
- Patients unable to return for the recall appointments

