7.2 Study Size

There will be a maximum total of 80 monolithic, high strength precrystallized lithium disilicate crowns (Quartz by Ivoclar Vivadent). There will be 2 groups of 40 crowns differentiated by occlusal thickness and type of cement.

- Group 1 = occlusal thickness of 1.5 mm delivered with a self-adhesive, self-curing resin cement (SpeedCem Plus/Ivoclar).
- Group 2 = occlusal thickness of 1.2 mm delivered with Adhese Universal Adhesive in total etch mode with a dual cure resin cement (Variolink Esthetic by Ivoclar Vivadent).

The study will be a randomized, longitudinal clinical study with the outcome data to be benchmarked against published results of other chairside CAD/CAM materials.

8 Data Collection

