8.3 Data Management

Case Report Form (CRF)

Castor EDC is a cloud-based Electronic Data Capture (EDC) platform which will be used to collect data. All changes are tracked by an audit trail. The pictures are stored locally at the University of Michigan. After entering data by a study coordinator the data will be reviewed and approved by the principal investigator

9 Statistical Analysis

After the clinical evaluation data is collected for baseline and each recall, the clinical ratings will be entered into a statistical management program and appropriate non-parametric tests will be run to verify significant differences. Each criterion-referenced category will be analyzed independently. At any given time period, significant differences in clinical evaluation ratings will be determined.

10 Project Time Line

The recruitment of patients and clinical placement of restorations will begin immediately upon approval and funding of the project. It is anticipated to take 10 months to recruit and deliver the restorations required for the study. The 1-year recall will occur in the second year of the study, and similarly for future recalls in that the 2-year recall will occur in the third year of the study and continuing. This will result in a total time of 6 years required to place and complete the 5-year recall of the restorations with an additional 9 months needed to complete the data analysis and final report for the project. Additional recall periods beyond the 5 years may also take place following approval by Ivoclar Vivadent.

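### Molars and premolars are both eligible, but the plan specifies neither allocation stratified by tooth type nor an analysis that uses it

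*Combined protocol and SAP*

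**What the plan says.** - **Eligibility (7.1).** The lesion or defective restoration is "to be restored on a maxillary or mandibular premolar or molar tooth". There is no quota or cap by tooth type.
- **The only tooth-type rule (7.1).** Where one patient has more than two acceptable teeth, "molar teeth will be included prior to premolar teeth". This decides which teeth of one patient enter the study. No reason is given for it.
- **Crowns per patient (7.1).** "No more than two restorations will be placed per patient".
- **Size and allocation (7.2).** "There will be a maximum total of 80 monolithic, high strength precrystallized lithium disilicate crowns", and "There will be 2 groups of 40 crowns differentiated by occlusal thickness and type of cement". The study is described as randomised, but the method, unit, blocking and stratification factors are not stated.
- **Analysis (Section 9).** Once the ratings are entered, "appropriate non-parametric tests will be run to verify significant differences", with each rating category taken separately. No test is named, and no covariate, stratified comparison or subgroup by tooth type is mentioned.

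**The concern.** The tooth to be crowned, and so its type, is known before allocation. Premolars and molars could plausibly differ in sensitivity, chipping and fracture, which are the subjects of aims 1 and 2 in Section 6. If they do, and chance puts more molars in one group, an analysis that ignores tooth type assigns part of that difference to the group. With 40 crowns per group, chance imbalances of several crowns are common and a few events can decide a comparison. Ignoring a prognostic factor also leaves its variation in the error term.

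The plan does not exclude using tooth type, but it commits nobody to it. Adjustment could then be adopted or dropped after the data have been seen.

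**Working it through.** **The plan's own figure.** The 80 crowns (40 + 40) cannot be reproduced, because no alpha, power, effect size or event rate is given. The check below takes 40 per group as fixed.

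**Inputs.** From 7.2: N = 80 crowns, n = 40 per group. Assumed: molar share 50-90%, outcome gap between molars and premolars 5-30 points, crowns allocated singly and independently without stratification. The documents give no molar share and no rates by tooth type.

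**Step 1: how often the groups differ in molars.** With M molars among 80 crowns, the number k in Group 1 is hypergeometric (80, M, 40). The difference between groups is 2k − M crowns, or (2k − M)/40 as a share. Its SD is (2/40) × √[40 × p(1 − p) × 40/79], with p = M/80. For p = 0.5 this is 0.05 × √5.063 = 11.3 points.

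| Molar share | M | SD (points) | P(6 or more molars, 15 points) | P(8 or more molars, 20 points) |
|---|---|---|---|---|
| 50% | 40 | 11.3 | 26.3% | 11.7% |
| 60% | 48 | 11.0 | 25.4% | 11.0% |
| 70% | 56 | 10.3 | 22.2% | 8.7% |
| 80% | 64 | 9.0 | 16.1% | 4.8% |
| 90% | 72 | 6.8 | 5.7% | 0.5% |

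**Step 2: the shift it causes.** Shift in the group difference = imbalance in molar share × outcome gap.

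| Outcome gap | 15-point imbalance | 20-point imbalance | 20-point imbalance, in crowns of 40 |
|---|---|---|---|
| 5 points | 0.75 | 1 | 0.4 |
| 10 points | 1.5 | 2 | 0.8 |
| 20 points | 3 | 4 | 1.6 |
| 30 points | 4.5 | 6 | 2.4 |

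**Step 3: effect on the unadjusted test.** Exact two-sided 5% type I error at 70% molars, chi-square test:

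| Molar vs premolar rate | Averaged over all allocations | Given exact balance | Given a 20-point imbalance |
|---|---|---|---|
| 10% vs 3% | 5.8% | 5.7% | 6.3% |
| 30% vs 10% | 5.0% | 4.5% | 6.5% |
| 40% vs 10% | 4.8% | 3.8% | 7.5% |

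Fisher's exact test averages 1.2-2.9% over the rates examined. The error is therefore controlled overall, and it varies with the imbalance actually drawn.

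**Step 4: scale.** The standard error of a difference in proportions is √[2 × p(1 − p)/40]. At a 10% event rate it is √0.0045 = 6.7 points. At 21% it is 9.1 points; 21% is 0.7 × 30%, the lowest overall rate compatible with a 30-point gap at 70% molars if molars are at higher risk. The largest shift in Step 2 is then 6/9.1 = 0.66 standard errors.

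**Step 5: two crowns per patient.** If patients rather than teeth are randomised, imbalance can be larger. In an illustrative extreme of 40 patients with two same-type crowns each, split 20/20, an 8-crown imbalance needs a difference of only 4 molar patients. Its probability is 34%, 33% and 30% at 50%, 60% and 70% molars.

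**The case against.** The strongest case against runs as follows.

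- **Silence is not exclusion.** Section 7.2 names no randomisation method and Section 9 no test. A stratified rank test is itself non-parametric, so Section 9 would permit it. This stands: the finding is that nothing is specified, not that the plan chose an unstratified method.
- **The priority rule is not evidence of prognosis.** A reader might infer that ranking molars first shows that the sponsor regards tooth type as affecting outcome. The documents do not support that. The rule applies only within a patient who has more than two acceptable teeth, and no passage links tooth type to chipping, fracture or sensitivity. Nor do the documents list tooth type as a recorded data field, although it must be known for a crown to be made.
- **Randomisation protects the test.** A reader might infer that the group comparison is biased or its error rate inflated. Step 3 shows otherwise: averaged over allocations, the error rate stays near or below 5%. What remains is conditional imbalance and lost precision.
- **The shift is small against the noise.** The extreme shift needs both a 20-point imbalance and a 30-point gap, and is still under one standard error. With an assumed 80% power and two-sided 5% level, 40 per group detects only differences such as 10% vs 36%. This stands and limits the severity.
- **The remedy has complications.** A patient with one molar and one premolar fits neither stratum if patients are randomised. A standard van Elteren test ignores pairing within patients. At 50-70% molars the premolar stratum holds about 12-20 crowns per group and may contain no fractures. These points do not defeat the remedy, but it has to deal with them.

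**Conclusion.** The point holds in a limited form. Both tooth types are eligible, and the plan specifies neither stratified allocation nor an analysis that uses tooth type. Under simple allocation, an imbalance of 15 points or more would arise in about one trial in four at 50-70% molars, one in six at 80% and one in eighteen at 90%. A 20-point imbalance would move the estimated group difference by 1-6 points.

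These sizes rest on an assumed molar share, an assumed 5-30 point outcome gap and independently allocated crowns. Randomisation by patient could make imbalance more frequent. If tooth type does not affect the outcome, there is no shift.

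A reader might also infer that balancing tooth type would let a group difference be read as an effect of thickness or of cement. It would not: the two groups in 7.2 differ in both at once, and that is a separate limitation. This is an inexpensive improvement to an under-specified plan, not a flaw that invalidates the comparison.

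**What to change.** **Section 7.2.** State whether the patient or the tooth is randomised. Allocate in permuted blocks stratified by molar/premolar. If patients are randomised, define in advance the stratum of a patient who contributes one of each, for example by the first study tooth. With teeth randomised in small blocks, the imbalance should stay at about 0-2 crowns (0-5 points).

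**Section 9.** Make the primary group comparison tooth-type-stratified or adjusted:
- for ordinal ratings, a van Elteren test or an ordinal model with a molar/premolar term;
- for chipping and fracture, a stratified exact or Cochran-Mantel-Haenszel comparison;
- in each case, state how two crowns in the same patient are handled, since the standard forms of these methods treat crowns as independent.

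**If allocation is already complete,** make the analysis change alone, and record it before outcome data are compared by group.

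**Cost.** One two-level factor in the allocation list and one term or stratum in the analysis, with no additional crowns, visits or procedures. The gain will be small if events are very rare or nearly all crowns are on molars.

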7.2 Study Size

There will be a maximum total of 80 monolithic, high strength precrystallized lithium disilicate crowns (Quartz by Ivoclar Vivadent). There will be 2 groups of 40 crowns differentiated by occlusal thickness and type of cement.

- Group 1 = occlusal thickness of 1.5 mm delivered with a self-adhesive, self-curing resin cement (SpeedCem Plus/Ivoclar).
- Group 2 = occlusal thickness of 1.2 mm delivered with Adhese Universal Adhesive in total etch mode with a dual cure resin cement (Variolink Esthetic by Ivoclar Vivadent).

The study will be a randomized, longitudinal clinical study with the outcome data to be benchmarked against published results of other chairside CAD/CAM materials.

8 Data Collection

8.1 Post-Operative Sensitivity

To evaluate the immediate post-operative sensitivity, patients will be contacted by telephone once a week after the initial appointment for four weeks or until the restoration is reported asymptomatic. A criterion-referenced rating scale will be used to measure sensitivity. The phone interview will be used as a follow-up procedure to minimize recall loss as the patient is not required to return to the clinic. During the phone interview a criterion-referenced rating will be made of functional tooth sensitivity using the following scale. Patients will only be asked to return for an evaluation if they are having continued discomfort or any indication of premature occlusal contact.

Sensitivity Criteria:

- 1= No sensitivity is experienced at anytime
- 2= Slight sensitivity is experienced occasionally but it is not uncomfortable
- 3= Moderate sensitivity is experienced intermittently and it is noticeably uncomfortable
- 4= Severe discomfort is noted routinely with cold or pressure stimulation

8.2 Clinical Evaluation

Two independent evaluators will examine all crowns in the study. Clinical evaluations will be made at baseline, six months, one year, two years, three years, four years, and five years using written criteria based on FDI criteria (Hickel et al., 2007 and 2010) (see Appendix for criteria description). Disagreements in evaluations will be discussed between the evaluators and a consensus judgment will be reached and recorded for every criteria.

Intraoral digital color pictures at a 1:1.5 magnification will be taken to document pre-operative, cavity preparation, and post-operative conditions. Facial and occlusal views of the tooth will be documented for both the pre-operative and post-operative conditions including occlusal contacts.

A post-cementation quadrant optical scan (CEREC PrimeScan) will be made of each test restoration at each recall visit. The scan will include the quadrant with the test crown, the opposing quadrant and buccal bite.

Bite-wing radiographs (BWXR) of each test tooth will be reviewed at the three-year recall. A new BWXR will be taken at the recall appointment at no cost to the patient if BWXR dated within 6 months of the three-year recall is not available for review. The use of

radiographs in the study is in compliance with the standard of care for ensuring and maintaining the health of the tooth during treatment and not for research-specific reasons.

8.3 Data Management

Case Report Form (CRF)

Castor EDC is a cloud-based Electronic Data Capture (EDC) platform which will be used to collect data. All changes are tracked by an audit trail. The pictures are stored locally at the University of Michigan. After entering data by a study coordinator the data will be reviewed and approved by the principal investigator

9 Statistical Analysis

After the clinical evaluation data is collected for baseline and each recall, the clinical ratings will be entered into a statistical management program and appropriate non-parametric tests will be run to verify significant differences. Each criterion-referenced category will be analyzed independently. At any given time period, significant differences in clinical evaluation ratings will be determined.

10 Project Time Line

The recruitment of patients and clinical placement of restorations will begin immediately upon approval and funding of the project. It is anticipated to take 10 months to recruit and deliver the restorations required for the study. The 1-year recall will occur in the second year of the study, and similarly for future recalls in that the 2-year recall will occur in the third year of the study and continuing. This will result in a total time of 6 years required to place and complete the 5-year recall of the restorations with an additional 9 months needed to complete the data analysis and final report for the project. Additional recall periods beyond the 5 years may also take place following approval by Ivoclar Vivadent.

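### Section 9 rests the comparison of the 1.2 mm and 1.5 mm protocols on significance tests alone; with 40 crowns per group, an excess of about 10 points in fractures would usually be non-significant

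*Combined protocol and SAP*

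**What the plan says.** - **Background (before Section 5).** An occlusal thickness of 1.5 mm is described as the general recommendation for glass ceramics. The new material "may allow a more conservative occlusal reduction resulting in a crown thickness of 1.2 mm".
- **Section 6, Aim 2.** "Evaluate the resistance to material chipping and fracture of reduced thickness high strength precrystallized lithium disilicate CAD/CAM crowns". The aim names no comparator, direction or hypothesis.
- **Section 7.2.** "There will be 2 groups of 40 crowns differentiated by occlusal thickness and type of cement". Group 1 is 1.5 mm with a self-adhesive cement. Group 2 is 1.2 mm with a total-etch adhesive and a dual-cure cement. The same section wants "the outcome data to be benchmarked against published results of other chairside CAD/CAM materials".
- **Section 9.** "appropriate non-parametric tests will be run to verify significant differences", and "At any given time period, significant differences in clinical evaluation ratings will be determined". No test is named, and each rating category is analysed on its own. The section gives no significance level, interval, margin or power statement, and no named analysis of fracture or chipping.

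**The concern.** Nothing in the background suggests that the thinner crown should fracture less; its stated attraction is a more conservative preparation. The useful question from the randomised comparison is therefore whether the 1.2 mm protocol comes acceptably close to the 1.5 mm protocol. A test for a difference does not answer that. It starts from no difference, and a non-significant result is what a small trial tends to produce. It also becomes more likely as crowns are lost to follow-up.

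The error that matters is to accept a protocol that fractures more often. Section 9 does not control that error. It also does not require the one result that would expose it: the size of the difference with its uncertainty.

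**Working it through.** **Inputs from the plan.** 40 crowns per group (Section 7.2); five years of follow-up (Section 5); at most two crowns per patient (Section 7.1). The plan has no power calculation to reproduce.

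**Assumptions.** Two-sided 0.05. A yes/no outcome per crown (chipped or fractured by five years). Independent crowns and no losses unless stated. The plan gives no fracture rates, so a range is used.

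**Step 1. Chance of missing an excess.** Section 9 names no test, so two are compared: Fisher's exact test (conservative) and the asymptotic Mann-Whitney test, which for a yes/no outcome is the uncorrected chi-square times (N−1)/N with N = 80. Power is the sum, over all pairs with more events y in Group 2 than x in Group 1, of Bin(x; 40, p1) × Bin(y; 40, p2) wherever p ≤ 0.05. Missed = 1 − power.

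| True rates, 1.5 mm v 1.2 mm | Power, Fisher | Power, Mann-Whitney | Missed |
|---|---|---|---|
| 2.5% v 10% | 9% | 29% | 71–91% |
| 2% v 10% | 11% | 34% | 66–89% |
| 5% v 15% | 18% | 35% | 65–82% |
| 10% v 20% | 16% | 25% | 75–84% |
| 0% v 10% | 21% | 58% | 42–79% |
| 5% v 20% | 41% | 57% | 43–59% |
| 0% v 15% | 57% | 87% | 13–43% |
| 5% v 25% | 65% | 76% | 24–35% |

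With an assumed 20% loss (32 per group), 5% v 15% is missed in 72% (Mann-Whitney) to 89% (Fisher) of trials.

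**Step 2. The choice of test matters at the boundary.** Take 0 v 5 fractures.
- Fisher: 2 × C(40,5)/C(80,5) = 2 × 658,008/24,040,016 = 0.055.
- Mann-Whitney: chi-square = 80 × (5 × 40)²/(40 × 40 × 5 × 75) = 5.33; × 79/80 = 5.27; p = 0.022.

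The same data are non-significant by one admissible test and significant by the other.

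**Step 3. What an interval would show.** The Newcombe upper limit is d + √[(u2 − p2)² + (p1 − l1)²]. Here d = p2 − p1 is Group 2 minus Group 1, u2 is the Wilson upper limit for Group 2 and l1 is the Wilson lower limit for Group 1.
- 0 in both groups: u2 = 1.96²/(40 + 1.96²) = 3.84/43.84 = 8.8%, so the upper limit is 8.8 points.
- 1 in Group 2, 0 in Group 1: 2.5 + (12.9 − 2.5) = 12.9 points.
- 0 in Group 2, 1 in Group 1: −2.5 + √[8.76² + (2.5 − 0.44)²] = −2.5 + 9.0 = 6.5 points.
- 6 in Group 2, 1 in Group 1: difference 12.5 points, interval −0.6 to 26.7. Fisher gives p = 0.11. Reporting only that p-value would hide an interval that reaches almost 27 points.

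**Step 4. How often a no-worse conclusion would be reached.** Take a 10-point margin purely as an illustration, equal true rates p, one-sided 0.025 and n = 40. Power ≈ Φ(0.10/√[2p(1 − p)/40] − 1.96). For p = 5%: 0.10/0.0487 − 1.96 = 0.09, so 54%. For p = 2% it is 89% (the approximation is rough there), and for p = 10% it is 32%.

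**The case against.** **No worse is not a declared hypothesis.** This stands. Aim 2 says only that resistance will be evaluated, and the background sets 1.2 mm beside the recommendation for full-contour zirconia, not beside Group 1. A reader might infer that the plan commits to a non-inferiority claim, or will present a non-significant test as equivalence. The documents say neither. The point is that Section 9 offers nothing that would prevent it.

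**The declared frame is a benchmark against published results.** This is true, but it does not replace the randomised comparison. Section 9 describes no benchmark analysis and sets no threshold for one.

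**The arithmetic depends on an assumed test and assumed rates.** This stands in part. A reader might infer that any large excess would go unnoticed. That is not supported: 5% v 25% is usually detected, 0% v 15% is detected in 57% to 87% of trials, and 0 v 5 fractures is significant by one of the two tests. Section 9 also analyses ratings on FDI-based criteria (Section 8.2), which need not be reduced to yes/no.

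**A non-inferiority rule is only one option.** This stands. Estimation with an interval and no pass/fail margin would also meet the concern. Nor can one say that 40 per group could never support a margin below about 9 points: 8.8 is the limit when neither group has a fracture, and it falls to 6.5 with a single fracture in Group 1 and none in Group 2.

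**Conclusion.** The concern holds in a limited form. Section 9 rests the comparison on tests for a difference, with no interval, while the rationale points to whether the 1.2 mm protocol is acceptably close. With 40 per group, an excess of about 10 points would usually be non-significant if the 1.5 mm rate is about 2% or more: 5% v 15% is missed in 65% to 82% of trials. At 15 points above 5% the answer depends on the test, and near 20 points detection is more likely than not. With a 1.5 mm rate near zero, even a 10-point excess may be found more often than not by Mann-Whitney (58%).

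These figures rest on assumed rates, a yes/no outcome, a two-sided 0.05 level and independent crowns with full follow-up. Losses make detection harder; the effect of clustering was not calculated.

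A reader might also take either analysis as a verdict on thickness. It cannot be one, because cement changes together with thickness in Section 7.2. Only the two combined protocols can be compared.

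**What to change.** Add to Section 9, for Aim 2:

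1. The outcome is the proportion of crowns chipped or fractured by five years. Report the difference (Group 2 minus Group 1) with a two-sided 95% confidence interval that accounts for up to two crowns per patient, and base the conclusion on that interval.
2. A p-value above 0.05 is not reported as equal, equivalent or no worse.
3. A claim of no worse is made only if the upper limit lies below a margin that the sponsor fixes and justifies before outcome data are seen. Otherwise the result is called inconclusive. If no margin is set, the interval is reported without such a claim.
4. State that with no fractures in either group of 40 the upper limit is about 9 points (Newcombe), and that the comparison is of combined thickness-and-cement protocols, not of thickness alone.

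The cost is SAP wording and, if a no-worse claim is wanted, one decision on the margin. No extra patients or visits are needed. The downside is a less favourable conclusion. Inconclusive is a likely result: at the illustrative 10-point margin it would occur in about 46% of trials if both true rates were 5%, and about 68% if both were 10%.

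### Section 9 gives one unadjusted test per criterion per visit, with no stated primary outcome, contrast, alpha or multiplicity rule, and no stated analysis spans the recalls

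*Combined protocol and SAP*

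**What the plan says.** Section 9 has three sentences. The first says that, once ratings for baseline and each recall are collected, "appropriate non-parametric tests will be run to verify significant differences". The second is "Each criterion-referenced category will be analyzed independently". The third is "At any given time period, significant differences in clinical evaluation ratings will be determined".

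The other relevant statements are outside Section 9:

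- **Visits (Section 8.2):** "Clinical evaluations will be made at baseline, six months, one year, two years, three years, four years, and five years". That is seven evaluations.
- **Groups (Section 7.2):** "There will be 2 groups of 40 crowns differentiated by occlusal thickness and type of cement". The same section says outcomes will be benchmarked against published results for other chairside materials. Neither comparison is tied to a test.
- **Aim 1 (Sections 6 and 8.1):** short-term sensitivity, rated by telephone on a four-point criterion-referenced scale. The schedule is "patients will be contacted by telephone once a week after the initial appointment for four weeks or until the restoration is reported asymptomatic".
- **Aim 2 (Section 6):** "Evaluate the resistance to material chipping and fracture of reduced thickness high strength precrystallized lithium disilicate CAD/CAM crowns".
- **Aim 3 (Section 6):** "Evaluate the longitudinal clinical performance of precrystallized lithium disilicate crowns over five years of clinical service".
- **Crowns per patient (Section 7.1):** at most two.

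The front matter and the Appendix describing the modified FDI criteria were not available to this review. All statements about what is missing refer to the remaining text.

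**The concern.** Section 9 does state a rule, and the rule is the problem. Testing every criterion separately at every time period, with no designated outcome and no adjustment, leaves open which result answers which aim. A nominal difference on one criterion at one visit could be reported as a finding, and nothing in the plan limits the chance that it is false.

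The contrast is also open. Group 1 v Group 2 is the natural reading of a randomized trial, but recall v baseline and observed v published are both compatible with the text. An analyst could choose among them after seeing the data.

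The tests also do not match the longest-running aim. Aim 3 is about performance over five years, while the only sentence in Section 9 on timing treats time periods one at a time.

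**Working it through.** **The plan's own figures.** There is no error rate to reproduce. The study size (at most 80 crowns, 40 per group) comes with no alpha, power, effect size or event rate, so it cannot be reproduced either.

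**Inputs from the document.** Seven evaluations (Section 8.2); 40 crowns per group (Section 7.2).

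**Inputs assumed for illustration.**

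- Contrast: Group 1 v Group 2, each test two-sided at 0.05.
- Number of criteria: 3 to 10. Aim 3 names three property groups (esthetic, functional, biological); the available text does not give the number of individual criteria.
- Correlation of 0.3 between criteria, and a range of correlations between visits.
- Crowns treated as independent.

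**Step 1: number of tests.** 3 × 7 = 21; 10 × 7 = 70.

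**Step 2: reference case, independent tests of exact size.** P(at least one false positive) = 1 − 0.95^m. For m = 21 this is 0.66; for m = 70 it is 0.97. Repeated ratings of the same crowns are not independent, so this case shows only the scale.

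**Step 3: correlated normal test statistics (simulation, 40,000 replicates).** The chance that any |z| exceeds 1.96:

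| Correlation between visits | 3 criteria | 10 criteria |
|---|---|---|
| 0.7 | 42% | 81% |
| 0.95 | 24% | 56% |
| 0.99 | 18% | 44% |
| Near 1 | 14% | 35% |

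In the last row each criterion contributes in effect one test, so the remaining excess over 5% comes from the number of criteria.

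**Step 4: rare adverse ratings, Fisher's exact test at 40 v 40 (simulated correlated crown ratings).** Fisher's test is conservative when events are few:

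| Adverse-rating rate | Correlation between visits | 3 criteria | 10 criteria |
|---|---|---|---|
| 10% | 0.7 | 25% | 62% |
| 5% | 0.7 | 8% | 22% |
| 5% | 0.99 | 3% | 10% |
| 2% | 0.7 | under 1% | under 1% |

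At a 10% rate and visit correlation 0.99 the chance is still about 12% to 34%. High persistence alone does not bring it below 5%; adverse ratings must also be uncommon.

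**Step 5: two crowns in one patient.** Suppose every patient contributes two crowns, with an assumed intraclass correlation (ICC), and a nominal 0.05 test ignores the pairing.

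- Both crowns in the same group: true size = 2(1 − Φ(1.96/√(1 + ICC))). This is 0.074 at ICC 0.2 and 0.110 at ICC 0.5.
- Crowns split between groups: true size = 2(1 − Φ(1.96/√(1 − ICC))). This is 0.028 at ICC 0.2 and 0.006 at ICC 0.5.

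The available text does not say whether patients or crowns are randomized, so the direction of this error is unknown.

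**The case against.** The strongest defence is that this is in substance a descriptive study. All three aims begin with the verb evaluate, and results are to be set beside published data. A wholly descriptive study would be legitimate, but Section 9 promises significance tests, so the defence points to one of the two possible remedies and does not remove the gap.

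Four further points limit what can be claimed:

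- **Aim 3.** A reader might infer that it requires a joint test over the recalls. It does not say so. An estimate across recalls would also serve, and the unnamed non-parametric tests could include a repeated-measures test. What stands is that no analysis spanning the recalls is stated.
- **Aim 1.** A reader might infer that sensitivity has no analysis at all. The text does not support this. The term criterion-referenced in Section 9 is also the term Section 8.1 uses for the sensitivity scale, so that sentence may cover it. The neighbouring sentences speak of baseline, recalls and clinical evaluation. Coverage is ambiguous, not absent.
- **Size.** The 66% to 97% of the independent case is tempting as a headline, but independence between repeated ratings of one crown is implausible. Only the seven visits and 40 v 40 come from the document, and the seven include baseline.
- **Missing parts.** The front matter might designate an outcome, and the Appendix should show how many criteria there are. Section 8.2 cites the Appendix for criteria descriptions, not statistics.

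**Conclusion.** The concern holds in this form: followed as written, Section 9 is one unadjusted test per criterion per visit. The available text has no primary outcome, contrast, deciding time point, alpha, multiplicity rule or stated analysis across the recalls.

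Under the assumptions listed, the chance of at least one false significant difference runs from about 81% (ten criteria, visit correlation 0.7) down to about 14% (three criteria, near-perfect persistence). With Fisher's test it can be under 1% if adverse ratings occur in only 2% of crowns. A reader might infer from these figures that this trial has a known, large false-positive rate. The documents do not support that, because the rate depends on the number of criteria, the rating distribution and the persistence of ratings, none of which they give. The conclusion that does not depend on these inputs is that the plan sets no bound. This should be corrected; confidence is medium because of the unavailable parts.

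**What to change.** In Section 9, before outcome data are seen:

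1. State the contrast as Group 1 v Group 2 at two-sided 0.05. Word it as thickness and cement together, since Section 7.2 varies both.
2. Name one primary comparison. An example is one pre-named modified FDI outcome over all recalls, in a single longitudinal ordinal or rank analysis that allows for two crowns in one patient. Ignoring the pairing makes the test too liberal if both crowns are in one group and too conservative if they are split.
3. Say which analysis answers Aim 1 and which answers Aim 2. Treat these as secondary, or adjust across the aims (for example Holm).
4. Report all other criterion-by-visit comparisons as exploratory, with estimates and confidence intervals and no significance claims.

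Alternatively, declare the study descriptive and replace the significance tests with estimates and confidence intervals.

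The cost is new text in Section 9, with no new data, visits or patients. The downside is that isolated differences at single visits can no longer be claimed as significant.
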